APPENDIX 2. MAJOR PROTOCOL DEVIATIONS

The major protocol deviations are defined in the following table:

PD header as per Protocol	Specific example database
Patient not meeting the following selection criteria (inclusion and exclusion) at screening but still included in the study	
Patients recruited in to the study violating the selection criteria
 
Insulin was initiated only after 6 months of T1DM diagnosis
 
Patient was on basal-bolus insulin therapy for at least 1 year before screening
 
Patient was on once daily Lantus® at stable dose
 
Lab criteria
 
Efficacy criteria - HbA1c
 
Safety criteria - ECG, Eye testing, Safety lab tests, Hb, LDL, TG, ALT, AST, Creatinine, Vital signs, HT
 
Other criteria - C peptide, BMI, infectious samples, drug abuse, Insulin resistance, age

Patient continued in the study despite meeting study discontinuation criteria	
Protocol specified withdrawal criteria
 
Withdrawal of consent
 
Use of prohibited medications [insulin, insulin analogs and other anti-diabetes medications as well as glucocorticoid therapy (oral, intravenous, inhaled or other routes that produce systemic effects)]
 
For female patients, diagnosis of pregnancy or a stated intention to become pregnant.
 
Repeated non-compliance as determined by the investigator in a consolidated overall evaluation of compliance
 
At the investigator's discretion, for safety issues such as severe hypoglycemia or hypoglycemic unawareness.
 
At the investigator's discretion, in certain situations such as significant intercurrent illness, hospitalization for surgery, or an SAE which in the opinion of the investigator warrants withdrawal.

Failure to perform tests or procedures which will impact the interpretation of key endpoints of the study	HbA1c not tested at screening, randomization, 12th and 24th week visit (all missed)
Patient not following treatment regimen mentioned in the protocol	
Patient was not given the assigned IP (instead of test medication, comparator medication was given)
 
Using insulin Glargine that is not IMP and part of the study during the study period

Study procedure issue	
Study completed without signing ICF
 
Sponsor unapproved IP used (temperature or humidity excursion prove.
 
For a patient recruited from Germany, Name, date of birth, or information

Document: \\JEEDC-NAS01A\Biosdata\Mylan\INSULIN_GLARGINE\UXA25824\Biostatistics\Documentation\SAP
 Author: [name] and [name] Version Number: Final V1.0
 Version Date: [27JUL2016]

Template No: CS_TP_BS016 – Revision 3
 Effective Date: 01May2012

Reference: CS_WI_BS005

	revealing patient identify was captured and it is not acceptable as per the German law
--	--

Document:	\\IEEDC-NAS01A\Biosdata\Mylan\INSULIN_GLARGINE\UXA25824\Biostatistics\Documentation\SAP	Version Number:	Final V1.0
Author:	[name] and [name]	Version Date:	[27JUL2016]

Template No: CS_TP_BS016 – Revision 3
Effective Date: 01May2012

Reference: CS_WI_BS005

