**Figure 1: Study Flowchart**

## 4. PATIENT SELECTION

### 4.1 Inclusion Criteria

Patients must meet all of the following inclusion criteria to be eligible for enrollment into the extension study:

1. Patients who have completed the 52-week treatment period (irrespective of their age at the completion of MYL-GAI-3001) of MYL-GAI-3001 and were assigned to Lantus® in that study.
2. Patients or their legal representatives must give written and signed informed consent before starting any protocol-specific procedures.
3. The patient is able and willing to comply with the requirements of the extension study protocol including the 8-point SMBG, completion of patient diary records as instructed and following a recommended diet and exercise plan for the entire duration of the extension study.
4. Female patients complying with the following:
  - Female patients of childbearing potential must be using oral contraception or two other acceptable methods of contraception, (e.g., intra-uterine device plus condom, spermicidal gel plus condom, diaphragm plus condom, etc.) from the time of randomization throughout the entire study.
  - Periodic abstinence (e.g., calendar, ovulation, symptothermal, post-ovulation methods) and withdrawal are not acceptable methods of contraception.
  - Postmenopausal females must have had no menstrual bleeding for at least 1 year prior to inclusion in MYL-1501D-3003 study.
  - Female patients who report surgical sterilization must have had the procedure at least 6 months prior to inclusion to MYL-1501D-3003 study.
  - All female patients of childbearing potential, must have negative pregnancy test results at baseline (week 0) and at each clinic visit as per the SCHEDULE OF ACTIVITIES.

- If female patients have male partners who have undergone vasectomy, the vasectomy must have occurred more than 6 months prior to inclusion in MYL-1501D-3003 study.

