#### **4.2 Exclusion Criteria**

Patients meeting any of the following criteria will not be included in the extension study:

1. History or presence of a medical condition or disease that in the Investigator's opinion would place the patient at an unacceptable risk from trial participation.
2. History of clinically significant (i.e., significant enough to alter the insulin dose requirement, as per the Investigator) acute bacterial, viral or fungal systemic infections in the 4 weeks prior to inclusion / randomization (recorded while collecting patient history) into MYL-1501D-3003.
3. Patients scheduled to receive another investigational drug during the extension study period.
4. Any major elective surgery requiring hospitalization planned during the extension study period.
5. Moderate insulin resistance, defined as requiring insulin (basal + prandial) of  $\geq 1.5$  U/kg/day (Lantus® in U/kg/day or Mylan's insulin glargine in IU/kg/day).

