9. DISPOSITION AND WITHDRAWALS

All patients who provide informed consent will be accounted for in this study.

The frequency and percentage of randomized patients who completed the trial or discontinued early will be summarized for each treatment sequence group. The comparison of patient discontinuations across treatment sequence groups will be performed using the Fisher's exact test. Reason for discontinuation from the study will also be summarized.

The number and proportion of patients withdrawing from the study during screening will be presented in a table. Additionally, the number and proportion of patients in each population will be summarized.

A listing of patients who did not meet the inclusion/exclusion criteria will be produced.

A list of significant protocol violations will be provided. A summary of significant protocol violations will also be provided as frequency and percentages, and treatment sequence group comparisons will be performed using the Fisher's exact test. Refer [Appendix 2](#) for significant protocol violation.

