15.1. PRIMARY EFFICACY

15.1.1. PRIMARY EFFICACY VARIABLE & DERIVATION

The primary efficacy outcome is change in HbA1c from baseline at week 36. .

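### SAP Appendix 2, on which the protocol-violation summary and Fisher test in SAP section 9 rest, does not match protocol v2.0 on selection criteria, the week-36 HbA1c, or prohibited and interfering drugs

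*SAP*

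**What the plan says.** SAP section 9 promises a list of significant violations, a summary ("A summary of significant protocol violations will also be provided as frequency and percentages") and a Fisher's exact comparison of the sequence groups. It sends the reader to Appendix 2 for what counts. Appendix 2 opens with "The major protocol deviations are defined in the following table". Its first column is headed as following the protocol; its second is headed as examples.

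The parts that matter here are:

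- **Selection row.** A general line, "Patients recruited in to the study violating the selection criteria", is followed by named items: timing of insulin start after diagnosis, prior basal-bolus therapy, stable once-daily Lantus, HbA1c, a group of safety tests, and "Other criteria - C peptide, BMI, infectious samples, drug abuse, Insulin resistance, age".
- **Missed-test row.** Its only entry is "HbA1c not tested at screening, randomization, 12th and 24th week visit (all missed".
- **Discontinuation row.** Prohibited-medication use is listed among withdrawal criteria said to come from the protocol.
- **Treatment-regimen row.** This covers receipt of the wrong study product and use of insulin glargine from outside the study.

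SAP section 1 states that the plan follows protocol v2.0. In that version, inclusion 1 (section 4.1) admits patients "irrespective of their age at the completion of MYL-GAI-3001", and exclusion 5 (section 4.2) reads "Moderate insulin resistance, defined as requiring insulin (basal + prandial) of" 1.5 U/kg/day or more. SAP 15.1.1 states: "The primary efficacy outcome is change in HbA1c from baseline at week 36". Protocol section 12 gives six kinds of significant deviation, the fifth being drugs that are prohibited or could influence key endpoints. Section 5.10 bars starting any Table 2 drug on treatment. Section 6.2 gives five withdrawal criteria.

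**The concern.** A deviation table is only as good as the rule that fills it. If Appendix 2 is applied as written, the comparison in SAP section 9 can count patients for features that this trial never made conditions of entry. It can also pass over two events that bear directly on the primary endpoint: a week-36 HbA1c that was not taken, and a glucose-modifying drug started on treatment. The trial is open-label and tests equivalence, with the per-protocol analysis as a planned robustness check (SAP 15.1.4), so a clear prior rule for deviations has some value. SAP section 3.3 declares two changes from the protocol and neither concerns deviations, so these differences are not announced departures.

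**Working it through.** No stated figure is in dispute. The check sets the texts side by side.

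**1. Selection criteria.** Protocol 4.1 has 4 inclusion criteria and 4.2 has 5 exclusion criteria, 9 in all.
- Insulin resistance (exclusion 5) is the only item named in the row that is an explicit criterion.
- Time to insulin start, HbA1c, C-peptide, BMI, drug abuse and age are not criteria. Inclusion 1 sets age aside expressly.
- ECG, eye, laboratory and vital-sign items can at most inform exclusion 1, the investigator's judgement of unacceptable risk.
- Completion of 52 weeks on Lantus in MYL-GAI-3001, contraception, another investigational drug and planned surgery are not named in the row. They are reached only through its general line. Recent systemic infection is also unnamed, unless the entry on infectious samples is credited to it. Missing consent is named, but in the study-procedure row.

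**2. HbA1c.** The Schedule of Activities has HbA1c at weeks 0, 12, 24 and 36. It has no separate screening visit, so screening and randomization are both read as week 0.
- Visits named in the row: weeks 0, 12 and 24, which is 3 of the 4. Week 36 is the one left out.
- A patient is flagged if week 0 AND week 12 AND week 24 are all untested.
- mITT requires a week-0 HbA1c AND a period 3 value (SAP 5.4). PP also requires a baseline and a period 3 value (SAP 5.5).
- Being flagged implies no week-0 value, which implies not in mITT and not in PP. The row cannot flag anyone in either set.
- A patient tested at weeks 0, 12 and 24 but not at week 36 is not flagged. SAP 5.4 places period 3 after week 24, so week 36 is its only scheduled HbA1c. Without an exit or unscheduled sample, that patient drops out of mITT, and the row does not record the missed test.

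For scale, the sample-size section allows for 10% of patients without baseline and last-period HbA1c: 0.10 × 138 = 13.8, about 14. Any of them with one result at week 0, 12 or 24 would escape the row. This is a planning allowance that includes withdrawals, not a forecast of missed tests.

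**3. Medication and withdrawal.** Items 1 to 4 of protocol section 12 correspond to the first four headers of Appendix 2. Item 6 (GCP) is closest to the study-procedure header. Item 5 has none, so 5 of the 6 have a header.
- Non-study insulin glargine is caught in the treatment-regimen row.
- Other insulins, other anti-diabetes drugs and systemic glucocorticoids appear only in the row for patients kept in the study after meeting a discontinuation criterion.
- That row treats prohibited-drug use as a protocol withdrawal criterion. It lists 6 criteria against 5 in protocol 6.2, and prohibited-drug use is the extra one.
- Table 2 drugs started on treatment are not named.

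**The case against.** The best defence is that both lists are illustrative. Protocol section 12 introduces its six items as examples, and the second column of Appendix 2 is headed as examples. The headers are broad: the one above the HbA1c entry would cover a missed week-36 test, and the selection row has its general line. Protocol section 12 also requires every significant deviation to be reported in the study report, whatever the appendix says. This stands, and it limits the weight of the point. It does not remove it, because the appendix says that it defines the deviations and one of its entries is a specific rule with the wrong visits.

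Other safeguards also count. SAP section 9 summarizes the number of patients in each population. Concomitant medications are listed (protocol 9.6), and those used by at least 10% are compared between groups. These show that a patient is missing or that a drug was taken; they do not classify either as a deviation. No extension-study threshold is given for HbA1c, C-peptide, BMI or age, so those entries flag nobody without a limit from elsewhere. That lowers the risk of false counts but leaves the entries unusable. SAP section 10 does plan to report C-peptide at baseline, which does not make it a criterion.

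Three stronger readings are tempting. A reader might infer that prohibited drugs are captured only among patients who continued after a discontinuation criterion; the treatment-regimen row, which catches non-study insulin glargine, shows otherwise. A reader might infer that Appendix 2 sets the PP population; SAP 5.5 does not cite it and has deviations affecting the primary outcome documented separately and signed off before lock. A reader might infer that true violations will go unreported; the broad headers and the protocol's reporting duty do not support that.

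**Conclusion.** The mismatch is real and is wrong as written, not merely short of detail. The selection row names non-criteria, the HbA1c row omits the primary endpoint visit and cannot flag anyone in mITT or PP, and section 12 item 5 has no row. The drug and withdrawal discrepancies share one line, so they count as one problem with two sides.

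The size is modest. The primary mITT analysis and its confidence interval do not change. The direct effect is on the violation listing, summary and Fisher test. An effect on PP is possible only if the pre-lock reviewers use Appendix 2 as their guide, which the documents do not say. The conclusion rests on a literal reading of Appendix 2 and on taking screening and randomization as week 0. If screening meant an additional parent-study test, the HbA1c row would be narrower still.

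**What to change.** Before database lock, amend SAP Appendix 2:

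1. Replace the named items in the selection row with the criteria of protocol 4.1 and 4.2.
2. Restate the HbA1c row as: baseline HbA1c not available, or week-36 HbA1c not performed in a patient still under follow-up at week 36. Say that this includes patients off treatment who are followed per the Schedule of Activities under protocol 6.2, since items 4 and 5 there keep such patients on the schedule to week 40.
3. Add a row for protocol section 12 item 5, covering prohibited drugs and Table 2 drugs started during treatment, whether or not the patient continued.
4. Reconcile the withdrawal row with protocol 6.2.

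Before the new row is used, Table 2 must also be reconciled with other protocol text. It lists glucagon and oral contraceptives, while protocol 7.5.6.3 provides for glucagon in severe hypoglycemia and inclusion 4 provides for oral contraception. This review takes no view on which rule is right.

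The cost is minor SAP text editing with no new data. Reported deviation counts may change; the primary analysis does not.
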